## Statistical Analysis Plan Template

Sponsor:	ProQR Therapeutics		
Protocol:	PQ-110-002		
Document Version No.:	1.0	Document Date:	04 JAN 2022

in study PQ-110-002 (in a maximum time-window of 1 month before dosing). If only one observation is available on or prior to the subject's first dose, that observation will be used as the pre-dose baseline value. For mobility course, FST and OCT, the data most recently collected prior to the subject's first dose of study treatment in study PQ-110-002 will be used as the pre-dose baseline value.

- For other efficacy endpoints collected on the eye level, the baseline 002 will be used.

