### 4.2.4. Definition of Baseline

For the endpoints collected on the subject level, the screening visit value in study PQ-110-002 will be defined as Baseline 002 values. For the endpoints collected on the eye level, there are three types of baseline values used for study PQ-110-002:

- Baseline 001: for BCVA, it is defined as  
for mobility course and FST, the average of measurements at pre-dose in study PQ-110-001 is considered as baseline 001.
- Baseline 002: for BCVA, it is defined as  
; for mobility course and FST, it's defined as the average of last two measurements only if the interval between them is up to 1 month before entering study PQ-110-002. Otherwise the most recent value will be taken as baseline 002. For the other endpoints, the screening value in study PQ-110-002 is used as baseline 002 value.
- Pre-dose Baseline: the efficacy endpoints collected on the eye level except BCVA, mobility course and FST, the baseline 002 will be used. For BCVA, mobility course and FST, Baseline 001 values are used for the first treated eye, non-treated contralateral eye as well as both eyes. For treated contralateral eye,
  - For BCVA, the baseline result corresponds to the best of the two most recent BCVA values available before the first dose of treatment with sepofarsen in that respective eye

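### The SAP ties the FST, mobility and OCT baseline of a treated contralateral eye to the subject's first PQ-110-002 dose in either eye, and does not average two qualifying FST or mobility readings

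*SAP*

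**What the plan says.** SAP 4.2.4 defines three baselines for eye-level endpoints.

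- **Baseline 001**, mobility course and FST: "the average of measurements at pre-dose in study PQ-110-001 is considered as baseline 001".
- **Baseline 002**, mobility course and FST: "the average of last two measurements only if the interval between them is up to 1 month before entering study PQ-110-002"; otherwise the latest single value.
- **Pre-dose Baseline**, for BCVA, mobility and FST: first treated eyes and non-treated contralateral eyes use Baseline 001. Treated contralateral eyes have their own rules.

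For a treated contralateral eye, BCVA is "the best of the two most recent BCVA values available before the first dose of treatment with sepofarsen in that respective eye", with the limit "in a maximum time-window of 1 month before dosing". The next rule begins "For mobility course, FST and OCT, the data most recently collected prior to" and ends "the subject's first dose of study treatment in study PQ-110-002 will be used as the pre-dose baseline value". It has no averaging, no window and no mention of the eye.

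On timing, Protocol 7.2 and SAP 4.2.10 place the contralateral eye's first dose on Day 1 and the first treated eye's dose 3 months later. Protocol 4.2 and SAP 2.1 allow the between-eye interval to be adapted and leave the start of contralateral treatment to a case-by-case decision. SAP 4.7.1 plans a separate summary of adverse events in treated contralateral eyes before their first dose in the study.

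SAP 4.8.3 runs an FST responder analysis on contralateral eyes treated in this study, with cut-offs of -0.5 and -0.7 log cd/m2.

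**The concern.** Two features of one sentence differ from the rules around it.

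The first is the anchor. Read literally, the subject's first dose is the earlier of the two eyes' first doses in PQ-110-002. If that is the first treated eye's dose, the contralateral eye's baseline is frozen at that date, however much later the eye itself is treated. Any change in the untreated interval is then reported as change on treatment. A programmer would have no textual ground for doing otherwise, because the BCVA rule shows that the SAP words an eye-specific anchor when it wants one.

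The second is the missing average. For FST and mobility, the treated contralateral eye is the only group whose pre-dose baseline is a single visit's value even when two qualify. A noisier baseline makes change from baseline noisier. The FST responder analysis is run on exactly these eyes, and with at most 11 subjects (Protocol 5.1) one eye moves the rate by at least 1/11, about 9 percentage points. The SAP gives no reason for the difference.

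**Working it through.** The plan states no figure on this point, so there is none to reproduce.

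**Anchor.** Let C and F be the months of the first PQ-110-002 dose in the contralateral and first treated eye. The literal anchor is min(C, F), so its distance from the contralateral eye's own dose is C - min(C, F).

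- Planned order, C = 0 and F = 3: 0 - 0 = 0 months.
- First treated eye dosed first, F = 0, with C = 3, 6 or 12 (illustrative): 3, 6 or 12 months.
- Both deferred, C = 6 and F = 3: 6 - 3 = 3 months.

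An eye-specific anchor makes the distance 0 in every case. Fresher data should usually exist in the deferred cases: visits are every 3 months (Protocol 7.1), and both eyes are assessed even when the contralateral eye is untreated (Protocol 4.2.1.3). The schedule of events is not in the public text, so the exact FST and mobility visits cannot be confirmed.

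**Averaging.** Inputs from the SAP: FST cut-offs c = 0.5 and 0.7 log cd/m2 of improvement (4.8.3). Assumptions: visit-to-visit SD sigma of 0.2 to 0.5 log cd/m2 (none is given in the documents), independent normal errors, no true change, and change measured from the Pre-dose Baseline (4.8.3 says only that it is from baseline). One FST value here means one visit's result, already averaged over stimulus sizes.

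With k baseline visits averaged, Var(change) = sigma^2 (1 + 1/k). That is 2 sigma^2 for k = 1 and 1.5 sigma^2 for k = 2: a 25% lower variance, and an SD lower by 1 - sqrt(0.75) = 13.4%. The false-responder probability is Phi(-c / (sigma sqrt(1 + 1/k))).

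Example, c = 0.5 and sigma = 0.3: k = 1 gives Phi(-0.5/0.424) = 11.9%; k = 2 gives Phi(-0.5/0.367) = 8.7%.

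| sigma | -0.5 log: one visit → two | -0.7 log: one visit → two |
|---|---|---|
| 0.2 | 3.9% → 2.1% | 0.7% → 0.2% |
| 0.3 | 11.9% → 8.7% | 4.9% → 2.8% |
| 0.4 | 18.8% → 15.4% | 10.8% → 7.7% |
| 0.5 | 24.0% → 20.7% | 16.1% → 12.7% |

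If all 11 possible eyes had two readings and none truly changed, the chance of at least one false responder at -0.5 log is 1 - (1 - p)^11: 35.1% → 20.5% at sigma 0.2, and 75.3% → 63.2% at 0.3. The expected number at sigma 0.3 goes from 11 × 0.1193 = 1.31 to 11 × 0.0868 = 0.95.

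**OCT.** 4.2.4 assigns OCT twice. The opening of the Pre-dose Baseline paragraph excepts only BCVA, mobility and FST, so OCT takes Baseline 002, the screening value. The later sentence puts OCT with mobility and FST under the most-recent-value rule. The two differ whenever a reading falls between screening and the first dose.

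**The case against.** The strongest reply is that the anchor is loose drafting. The sentence sits under a lead-in about the treated contralateral eye. The BCVA rule, whose anchor is the time "before the first dose of treatment with sepofarsen in that respective eye", itself falls back on the subject's first dose when only one observation exists. On the planned schedule the distance is zero, and the documents do not show how many eyes, if any, departed from it. This stands as a limit on the size of the problem. It does not remove the problem: no readable text says that the two phrases mean the same thing, and the SAP itself provides for on-study time before the contralateral eye's first dose.

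A reader might infer that an out-of-date baseline inflates the responder count. The documents do not support that. Protocol 2.0 describes gradual loss of the vision that remains; in a worsening eye an older baseline tends to be the better one, which makes improvement harder to show. No rate of drift is given, so neither direction can be assumed. The percentages above concern averaging only.

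On averaging, the single latest value lies within the protocol's own baseline definition (Protocol 10.4). Only one pre-dose assessment is required (Protocol 4.2.1.1), so a second reading within a month may often be missing. For those eyes averaging changes nothing, and the percentages are what it could achieve, not what it will. The analyses are descriptive, individual FST values are tabulated over time, and no responder comparison between groups of eyes is planned. All of this stands. What remains is that two qualifying readings are averaged under one FST and mobility rule and not under the other, without explanation.

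The mobility section (SAP 4.8.2) is blank in the public text, so a rule there cannot be checked.

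**Conclusion.** The point holds in a limited form. The anchor wording does nothing on the planned dosing order. If the first treated eye is dosed first, it dates the baseline by the full between-eye delay, discards later pre-dose data and misstates change from baseline by an unknown amount in an unknown direction. It should be corrected because deferral is foreseeable and the literal text would then govern.

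The averaging gap is a smaller loss of precision. For eyes with two qualifying readings, it lowers the per-eye false-responder rate by about 1.8 to 3.5 percentage points at -0.5 log and 0.5 to 3.5 points at -0.7 log, for sigma from 0.2 to 0.5. These figures rest on assumed SDs and independent errors. They bear on descriptive counts, not on a hypothesis test, and no size is claimed for mobility or OCT.

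**What to change.** Amend SAP 4.2.4 for treated contralateral eyes:

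1. For FST, mobility course and OCT, replace the reference to the subject's first dose with the first dose in that eye. Make the same change in the BCVA fallback.
2. For FST and mobility, apply the Baseline 002 rule to that anchor: average the last two readings if both fall within 1 month before that eye's first dose, otherwise take the most recent one. State the window in those terms, since the Baseline 002 sentence leaves it unclear whether the month applies to the gap between readings or to their distance from study entry.
3. Keep one rule for OCT, and remove the sentence that conflicts with it.
4. Name in SAP 4.8.3 the baseline that the responder analysis uses.

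The cost is SAP wording and the matching programming. No new assessments are needed. Eyes with one qualifying reading are unchanged by item 2, and eyes treated on the planned order are unchanged by item 1.

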### 4.2.5. **Adjustments for Covariates**

Adjustment for baseline BCVA will be applied for any inferential statistical analysis performed. If inferential statistical analysis will be requested at some point, this will be described in an addendum to this SAP.

### 4.2.6. **Multiple Comparisons/Multiplicity**

Adjustment for baseline BCVA will be applied for any inferential statistical analysis performed. If inferential statistical analysis will be requested at some point, this will be described in an addendum to this SAP.

### 4.2.7. **Subpopulations**

Subject-level summary tables will be generated featuring the following subpopulations:

- On-chart versus off-chart subjects. On-chart subjects are defined as subjects who can read letters on the ETDRS chart and for whom a logMAR value is available based on ETDRS in the logMAR category of  $< +1.7$  logMAR. Off-chart subjects are defined as subjects who cannot read letters on the ETDRS chart and for whom a logMAR value is available based on BRVT in the logMAR category of  $\geq +1.7$  logMAR.
- Adult ( $\geq 18$  years of age) versus pediatric ( $<18$  years of age) subjects
- Blue minus red FST response  $> 2 \text{ log cd/m}^2$  versus blue minus red FST  $\leq 2 \text{ log cd/m}^2$

## Statistical Analysis Plan Template

Sponsor:	ProQR Therapeutics		
Protocol:	PQ-110-002		
Document Version No.:	1.0	Document Date:	04 JAN 2022

### 4.2.8. Discontinuations from Study Drug and Discontinuations from the Trial

If the subject stops treatment for any reason, in general, the subject will be encouraged to remain in the study for observation for at least 3 months post last dose (see Protocol Section 4.2.2).

Subjects who discontinued from the trial will not be replaced as this is an extension study.

### 4.2.9. Missing, Unused, and Spurious Data

Missing data are defined as values that are not available and that would be meaningful for analysis if they were observed. Information that explains why data is missing data, including the relationship to COVID-19, will be captured in the electronic case report form and summarized in the clinical study report.

Missing data handling for mobility course composite score, BCVA and FST data is described in Section 4.2.9.1, 4.2.9.2. No imputation methods are planned for missing data for other efficacy endpoints or for safety data, except for partial or missing dates for the start and end of adverse events and for the use of concomitant medications, as described in Sections 4.2.9.3 and 4.2.9.4. The planned approach to handle partial and missing start dates for AEs and concomitant medications is conservative, in that the imputation is designed to impute a start date to occur within the period following the first dose of study treatment, rather than in the screening period. The planned approach to impute partial and missing end dates for AEs and concomitant medications is also conservative, as the imputed dates are fixed at the latest plausible date given the available information for that data record and the timing of the individual subject's visits.

#### 4.2.9.1 Missing data in Central Reading Center Mobility Course Composite Score

Missing course composite scores from the central reading center will be imputed as follows for the mobility course analyses:

- The reading center may not receive a video of the subject navigation attempt, or the video of the navigation attempt may be marginalized due to technical error, resulting in an inability to grade the navigation attempt. Marginalization of a video can occur due to lack of infra-red (IR) used on one or both cameras, truncated recording on one or both cameras, or one or both cameras recording out

## Statistical Analysis Plan Template

Sponsor:	ProQR Therapeutics		
Protocol:	PQ-110-002		
Document Version No.:	1.0	Document Date:	04 JAN 2022

of focus. In these instances, the reading center graders cannot grade the video with maximum accuracy, resulting in missing data, and the site score will be used to impute the central reading center score.

- An error in site level grading results in the early termination of the mobility test, before a pass occurs: The site technicians may grade the navigation attempt a “pass” and conclude the test prematurely (no video available), whereas the review from the reading center may identify the final navigation attempt as a “fail”. Therefore, a passing light level would not be identified by the reading center, resulting in missing data. In this case the following imputations will be used:
  - Last observation carried forward within the given eye (OD, OS, or OU) from prior visit.
  - In the event that imputing the last observation carried forward would result in the imputation of a pre-treatment score to a post-treatment time point, the following imputation will be used: the site level course composite score minus 1. This is the next easiest course / light level score. The next easiest score is defined as the score associated with passing the subsequent light level that would have been tested had the site correctly graded the navigation test as a fail and continued testing at the next light level. If, after the above imputations are applied, the composite score is still missing (e.g., for other reasons such as a visit not having been conducted), then the composite score will be treated as missing for analysis.

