#### 2.5.2. Efficacy Endpoints

##### 2.5.2.1. Secondary Endpoints

Secondary endpoints include:

- Change from baseline in BCVA
- Change from baseline in Mobility course score (unilateral and binocular)
- Change from baseline in photoreceptor outer segment layer thickness by optical coherence tomography (OCT) (if applicable)
- Change from baseline in OCI
- Change from baseline in Full-FST (blue and red stimuli; white at Investigator discretion) (thresholds)
- Change from baseline in PROs as measured by:
  - Visual Function Questionnaire-25 (VFQ-25) score (adult subjects), or
  - Cardiff Visual Ability Questionnaire for Children (CVAQC) score (pediatric subjects)
- Change from baseline in Pupillary Light Reflex (PLR) (latency and amplitude)

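### When the reading centre overturns a site pass on the mobility course, uncapped LOCF can impute a score at or above the level just failed, which masks decline

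*SAP*

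**What the plan says.** SAP 4.2.9.1 separates two causes of a missing reading-centre composite score. In the first, the video is absent or ungradable and the site score is substituted. The second is at issue here: the site grades an attempt a pass and ends the test, but "the review from the reading center may identify the final navigation attempt as a" fail. The SAP then states that "a passing light level would not be identified by the reading center, resulting in missing data".

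For this second cause the SAP sets an order:

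- First choice: "Last observation carried forward within the given eye (OD, OS, or OU) from prior visit".
- Only if carrying forward "would result in the imputation of a pre-treatment score to a post-treatment time point": "the site level course composite score minus 1. This is the next easiest course / light level score". The SAP explains this as the score for the level that would have come next "had the site correctly graded the navigation test as a fail and continued testing at the next light level".

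The affected endpoint is listed in SAP 2.5.2.1: "Change from baseline in Mobility course score (unilateral and binocular").

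**The concern.** A visit of this kind is not empty. It holds a centrally graded failure at a known level. The fallback uses that observation; the first-choice rule discards it. Carrying the prior score forward can therefore give a value that an observation at the same visit contradicts.

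The consequence depends on which eyes it falls on. First treated eyes were already dosed in PQ-110-001 (SAP 4.2.2). If pre-treatment means before that eye's first dose, their prior visits are post-treatment and uncapped LOCF is the usual rule for them. They are also the eyes with the longest treatment history, so they weigh heavily in the protocol's secondary objective of long-term and sustained efficacy (Protocol 3.2). A rule that records a decline as no change works against that objective.

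**Working it through.** The plan states no figure on this point, so there is none to reproduce. The check is a logical one, followed by an illustration of size.

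**Inputs from SAP 4.2.9.1**

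- S = site score, the level the site passed and the reading centre failed.
- L = prior-visit score for the same eye, the LOCF value.
- Direction: subtracting 1 gives an easier level, so higher is better.
- Bound: a correct fail would have moved testing to the next, easier level. The best score consistent with the failure is therefore S − 1.

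**Logic**

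- LOCF conflicts with the observed failure when L ≥ S.
- Excess over the bound in a conflict = L − (S − 1). The true overstatement is at least this, because the subject might also have failed level S − 1.
- When L = S − 1, LOCF equals the fallback. When L < S − 1, LOCF lies below it and may understate the eye.

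With S = 8, so that the bound is 7:

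| L | LOCF | S − 1 | min(L, S − 1) | Conflict | Excess over bound |
|---|---|---|---|---|---|
| 6 | 6 | 7 | 6 | no | none |
| 7 | 7 | 7 | 7 | no | none |
| 8 | 8 | 7 | 7 | yes | 8 − 7 = 1 |
| 9 | 9 | 7 | 7 | yes | 9 − 7 = 2 |
| 10 | 10 | 7 | 7 | yes | 10 − 7 = 3 |

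**Effect on recorded change.** Take L = 10 and a site error of exactly one level, so that the true score is S − 1. True declines of 1, 2, 3 and 4 levels give S = 10, 9, 8 and 7. LOCF records a change of 0 each time; S − 1 records −1, −2, −3 and −4. With no decline (S = 11) the two rules agree.

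**Illustrative model (all settings assumed).** Prior score L = round(N(0, SD)); true score T = round(N(−decline, SD)); S = T + 1. The ranges run over SD = 1 and SD = 2 levels.

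| True change | P(L ≥ S) | Mean excess, conflict visits only | Mean LOCF error, all affected visits | Mean error of min(L, S − 1) |
|---|---|---|---|---|
| 1-level improvement | 15%–30% | 1.3–2.3 | −1.0 | −1.2 to −1.7 |
| Stable | 36%–43% | 1.5–2.6 | 0.0 | −0.56 to −1.13 |
| 1-level decline | 57%–64% | 1.9–3.0 | +1.0 | −0.2 to −0.7 |
| 2-level decline | 70%–85% | 2.4–3.4 | +2.0 | −0.05 to −0.4 |

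In stable eyes LOCF is also below the true score in 36%–43% of visits, which is why the mean error is zero. The model sets T = S − 1, so the fallback has no error by construction; the table is not evidence that S − 1 is unbiased.

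**Effect on a group mean.** One affected eye with excess e shifts a mean over n eyes by e/n. At the maximum of 11 subjects, e = 1 to 3 gives 1/11 = 0.09 to 3/11 = 0.27 levels. At an assumed group size of 4 it gives 1/4 = 0.25 to 3/4 = 0.75 levels.

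**The case against.** The strongest reply is that LOCF is not biased in general. In the model its mean error in stable eyes is zero, and in an eye that has improved by one level it understates by one level on average. Improvement is a realistic case, because contralateral eyes start treatment in this study. That stands. A reader might infer that the error always favours the product; the SAP rule does not imply this. The error is upward only where L ≥ S, and a net upward bias needs a real decline. The excess of 1.5 to 3.4 levels for stable and declining eyes is likewise conditional on conflict and should not be quoted as the average effect of the rule.

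The alternatives also have costs. S − 1 credits a pass at a level never attempted, and it exceeds LOCF whenever L < S − 1. The rule min(L, S − 1) never contradicts the failure, but it is biased downward in stable and improved eyes. This also stands, and it argues against making min(L, S − 1) the main rule.

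Finally, the practical effect may be small. The trigger is one subtype of missing score with no stated frequency, in at most 11 subjects, for a secondary endpoint analysed descriptively. That limits the weight of the point. It does not remove the inconsistency between two rules in the same section, one of which uses the observed failure while the other ignores it.

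**Conclusion.** The point holds in this form: as written, the first-choice rule can assign a score at or above a level centrally graded as failed at the same visit. When it does, it overstates the eye by at least L − (S − 1) levels. That conclusion follows from SAP 4.2.9.1 alone and needs no assumed figure. The rule masks decline and does not inflate scores across the board: mean error is about 0 in stable eyes, +1 after a 1-level decline and +2 after a 2-level decline. Those sizes, and the conflict percentages, rest on the assumed SDs of 1 to 2 levels and a one-level site error.

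Two things cannot be settled from the documents. The frequency of overturned passes is not given. SAP 4.8.2 (Mobility Course) has no readable text in the public copy, so the score range and any sensitivity analysis there cannot be checked; it should not be inferred that none exists. No formal test or primary endpoint depends on the rule. The amendment is worth making, but nothing in the primary safety analysis turns on it.

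**What to change.** In SAP 4.2.9.1, for the overturned-pass scenario, make "the site level course composite score minus 1" the imputation for all visits and drop LOCF as first choice. No imputed score can then reach the failed level. Alongside it:

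- report observed-case mobility results without imputation;
- give min(L, S − 1) as a conservative sensitivity analysis, stating its downward bias in stable and improved eyes;
- keep pure LOCF at most as a further sensitivity analysis;
- report how many visits, by eye, were imputed under this rule.

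The cost is a line of SAP text and modest programming, with no new data and no effect on subjects. The downside to state openly is that S − 1 is an upper bound, since the next level was never attempted, and that it will sometimes be higher than the LOCF value it replaces.
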